4. After the informed consent is obtained with the patient's signature, the eligibility process begins. If the patient is deemed eligible, then the patient can participate in any study related procedures.
5. Interested patients must meet with a medical oncologist prior to study entry to determine if Oncotype Dx testing is recommended. If recommended and the patient is amenable to the possibility of receiving chemotherapy, there must be adequate biopsy tissue for testing. If adequate tissue is not available for the Oncotype Dx testing, patients may undergo additional biopsies. If a patient plans to decline chemotherapy, regardless of a high Oncotype Dx results, and elects to forgo the test, they will still be eligible for enrollment. If the patient elects to undergo an additional biopsy, but no residual tumor is found, then, the patient is not eligible for the study.
6. The Oncotype Dx assay is obtained initially in order to know which patient would benefit from the addition of adjuvant chemotherapy after her surgery, so that all patients undergo the appropriate standard-of-care postsurgical treatment. Treatment with neoadjuvant endocrine therapy is likely to induce changes within tumor biology and Oncotype Dx assay done after surgery in this setting may not provide reliable results, and thus, will not be performed after surgery.
7. Once enrolled, patients would be treated with the current standard-of-care endocrine therapy. Choice of endocrine therapy (aromatase inhibitors or tamoxifen) would be decided by medical oncologist, following a review of the patient's medical history and menstrual status. The patient would be treated with

endocrine therapy in a neoadjuvant setting for four weeks (+/- 1 week), with dosing continuing until surgery (+/- 2 days).

8. Patient compliance would be monitored by providing a calendar sheet to the patients to log in their daily use of prescribed endocrine therapy (Appendix.1). This calendar sheet will be returned to our clinical trial staff upon completion of the four-week (+/- 1 week) period of neoadjuvant endocrine treatment.

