2. One H&E slide and up to 15 to 20 unstained slides charged and cut at 4 microns thick will be reserved for study labs/biomarkers for pre and post-treatment assessments. These will be sent to **[name]** laboratory ([name]) at the **Medical College of Wisconsin Translational and Biomedical Research Center (TBRC)**.
3. Protein expression will be quantified on slides, using optimized immunohistochemical protocols for planned study biomarkers.

4. Ki-67 assessment on pre- and post-treatment specimens would include assessment by manual counting of stained tumor cells by our pathologists (dual stain CD45/Ki-67 to differentiate between lymphocytes and tumor cells and allow accurate counting of stained tumor cells), as well as quantitative immunohistochemistry.
5. Any residual tissue from pretreatment biopsy specimens and post-treatment surgical specimens would be stored at MCW Tissue Bank according to the MCW Tissue Bank quality control measures. The stored specimens would be deidentified.

Study Drugs

- Aromatase inhibitors: Anastrozole, Letrozole, Exemestane
- Tamoxifen

All agents are FDA approved for use in breast cancer patients and are similarly priced. Commercial stock will be used for this exploratory study.

Anastrozole

Anastrozole is a potent and selective nonsteroidal aromatase inhibitor.

Route of administration: Oral

Dose: 1 mg once daily. May be administered with or without food.

Dose adjustments: No dosage adjustment necessary in any degree of renal or hepatic impairment.

Letrozole

Letrozole is a potent and selective nonsteroidal aromatase inhibitor.

Route of administration: Oral

Dose: 2.5mg once daily. May be administered with or without food.

Dose adjustments:

- Renal impairment: No dosage adjustment necessary.
- Hepatic impairment:
 - Mild to moderate impairment (Child-Pugh class A or B): No dosage adjustment necessary.
 - Severe impairment (Child-Pugh class C) and cirrhosis: 2.5 mg every other day
 - Non-cirrhotic patients with elevated bilirubin: There are no dosage adjustments provided in the manufacturer's labeling (effect has not been determined).

Exemestane

Exemestane is an irreversible, steroidal aromatase inhibitor.

Route of administration: Oral

Dose: 25 mg once daily. Administer after a meal.

Dose adjustments: No dosage adjustment necessary in any degree of renal or hepatic impairment.

Tamoxifen

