5. Other less commonly reported side effects are anti-estrogen symptoms, i.e., hot flashes, mood changes and weight changes. Some of the rare but serious side effects, such as ischemic cardiovascular event, thromboembolic event or uterine cancer with tamoxifen are long-term side effects and are not expected to occur during this short course of neoadjuvant treatment. Similarly, decrease in bone density with aromatase inhibitors is a slow and long-term side effect, not expected to be seen during the four-week study period.
6. There are no dose modifications or reductions recommended with endocrine treatment.

VII. STATISTICAL CONSIDERATIONS

Statistical analyses:

Demographic and baseline characteristics, such as age, race, weight, values of all biomarkers pre and post-treatment, response measures will be summarized, using means, standard deviations, medians, ranges for continuous variables, and proportions for categorical variables.

This is an exploratory study to gather information on how frequently protein levels of HER growth factor receptors (HER1-4) are upregulated along with changes in other study biomarkers and correlation with Ki-67 in response to short-term neoadjuvant endocrine in early stage HR+ breast cancer. We hypothesize that expression of one or more HER proteins (HER1-4) will be upregulated in at least 50% of tumors after four weeks of neoadjuvant endocrine therapy and this upregulation will correlate with Ki-67 expressed in more than 10% of cancer cells, as compared to upregulation in 30% or less of tumors without the therapy. The change in Ki-67 expression will be dichotomized, as a categorical variable with $\geq 10\%$ increase coded as high and $< 10\%$ coded as low.

- a) For the primary outcome: An exact binomial one sample test of proportions will be used for to test the hypothesis that proportion of upregulated HER proteins will be at least 50% after therapy versus the null hypothesis that the proportion of upregulated HER proteins is not greater than 30%.
- b) For analyzing - the differences in proportion of upregulated HER proteins between the high difference in Ki-67 and low difference in Ki-67 groups, two sample tests of proportions will be used.

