Appendix 1. IIT-[name]-Endocrine: Monthly Intake Diary

Institution: _____ Physician: _____ Study ID#: _____ Initials (L, FM): _____

Instructions for the participant: This is a monthly calendar on which you are to record the daily anti-estrogen pill you take each day for the 4-week period. If you develop any side effects from the pill, describe side effect on the day that it happened on the calendar below. If you ever miss taking a pill, write missed on the date. Please bring your calendars with you to your follow up visit after you've completed the 4-week period. If you take over the counter medications, for example cold & allergies, please write on the day what medication you took.

Special Instructions: Please take 1 anti-estrogen pill, ONCE each day, preferably in the morning with food & a glass of water. Tablets MUST be swallowed whole, do NOT crush or chew. AVOID grapefruit & products containing grapefruit juice while you are taking tamoxifen.

If you have any questions, please contact: **Phone:**

Patient Name: _____ **Date:** _____

Date:

Surgeon: **Surgery Date:**

Surgery Date:

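### For letrozole in severe hepatic impairment and cirrhosis the dosing passages conflict, and the patient diary's fixed four weeks does not match treatment that runs until surgery; the passages need reconciling

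*Combined protocol and SAP*

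**What the plan says.** **Study Drugs, Letrozole (Section IV).** The general entry is "Dose: 2.5mg once daily. May be administered with or without food". Under hepatic impairment there are separate lines: "Mild to moderate impairment (Child-Pugh class A or B): No dosage adjustment necessary" and "Severe impairment (Child-Pugh class C) and cirrhosis: 2.5 mg every other day". The other three agents carry no renal or hepatic adjustment.

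**Patient Assessments, item 6 (Section VI).** "There are no dose modifications or reductions recommended with endocrine treatment". The sentence covers endocrine treatment as a whole and has no qualifier.

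**Monthly Intake Diary (Appendix 1).** One form serves all agents. It instructs: "Please take 1 anti-estrogen pill, ONCE each day, preferably in the morning with food & a glass of water". It asks the patient to "record the daily anti-estrogen pill you take each day for the 4-week period". Its only agent-specific line is the grapefruit warning for tamoxifen.

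**Treatment Plan, item 7 (Section IV), repeated in Study Calendar footnote 9.** Treatment is given "for four weeks (+/- 1 week), with dosing continuing until surgery (+/- 2 days").

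**Study Drugs, Exemestane (Section IV).** "Dose: 25 mg once daily. Administer after a meal".

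**Eligibility (Section III).** Inclusion 18 caps ALT and AST at 3 x ULN and bilirubin at 1.5 x ULN. Inclusion 11 leaves suitability for endocrine treatment to the oncologist. Exclusion 5 removes patients whose condition would prevent protocol therapy. None of these mentions cirrhosis or Child-Pugh class.

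**The concern.** A site that meets a letrozole patient in the hepatic subgroup finds one schedule in Study Drugs, a statement in Section VI that no changes are recommended, and a patient form that asks for a daily tablet. The protocol does not say which governs, and exposure differs about two-fold between the readings.

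The duration wording bears on the endpoint specimen. The post-treatment HER and Ki-67 measurements come from the surgical specimen, and the Treatment Plan intends dosing to continue up to surgery. A form that describes treatment as a four-week period leaves it unclear to the patient what to do if surgery falls in week 5. Treatment Plan item 18 counts anyone with at least two weeks of therapy as evaluable, so a specimen taken after such a gap would still enter the analysis.

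**Working it through.** The plan gives no figure to reproduce here. The check is a comparison of passages, with simple counts to show the size.

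**1. Dose frequency, hepatic subgroup on letrozole.**

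| Place | What it implies for this subgroup |
|---|---|
| Study Drugs, Letrozole | 2.5 mg every other day |
| Section VI, item 6 | no change from the usual schedule, if read literally |
| Appendix 1 diary | one tablet daily |

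For every other letrozole patient the three places agree on once daily.

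Tablets over D days: D if daily; D/2 rounded up if every other day starting on day 1. Dose = tablets x 2.5 mg. D takes the shortest, planned and longest treatment: 4 - 1, 4 and 4 + 1 weeks.

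| D (days) | Daily | Every other day | Ratio |
|---|---|---|---|
| 21 | 21 (52.5 mg) | 11 (27.5 mg) | 21/11 = 1.9 |
| 28 | 28 (70 mg) | 14 (35 mg) | 28/14 = 2.0 |
| 35 | 35 (87.5 mg) | 18 (45 mg) | 35/18 = 1.9 |

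**2. Can such a patient enrol?** The enzyme and bilirubin limits make it unlikely but do not exclude cirrhosis or a Child-Pugh class by name. Neither the Study Calendar nor the screening list in Section V schedules a Child-Pugh assessment. Exclusion 5 does not settle it, because Study Drugs supplies a schedule for exactly these patients. Either they are eligible, and item 6 and the diary conflict with Study Drugs, or they are not, and the criteria do not say so. The number affected cannot be computed: the documents give neither the frequency of severe hepatic impairment nor the share of patients on letrozole.

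**3. Duration.** The protocol window is 21 to 35 days; the diary period is 28 days. The difference is up to 35 - 28 = 7 days one way and 28 - 21 = 7 days the other. If, as an assumption, a patient took four weeks as the end and had surgery on day 35, the gap would be 7 days, against a tolerance of 2 days around surgery. On that assumption the tolerance is exceeded for surgery after day 28 + 2 = 30. Section V plans no clinic follow-up during treatment, though the treating physician may arrange one, so no scheduled contact would correct the misreading.

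**4. Food.** Exemestane is to follow a meal; the diary expresses a preference for taking the pill in the morning with food. These point the same way and differ only in firmness. This is minor.

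**The case against.** **Item 6 may concern toxicity only.** It closes a list on side effects in the adverse-event section, whereas the letrozole entry sets schedules by organ function. That is a fair reading and would remove the conflict between those two places. But the sentence does not limit itself in that way, and the reading leaves the letrozole entry and the diary in conflict.

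**The subgroup may be empty.** The laboratory limits, exclusion 5 and the oncologist's choice of agent after reviewing the history all make enrolment unlikely. The subgroup line may also mean class C together with cirrhosis, in which case cirrhosis with class A or B would fall under the line that requires no adjustment. This stands. A reader might infer that some patients would be dosed against the protocol; the documents support only that a patient could be.

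**The diary does not tell anyone to stop.** It describes a recording period, has a surgery-date field and refers to calendars in the plural. Treatment Plan item 8 describes the same sheet as returned after four weeks plus or minus one. This also stands. A reader might infer that the plan itself takes patients off drug before the surgical specimen; no passage gives that instruction, so the 7-day gap is a possible misreading and not a stated rule.

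**Some material cannot be seen.** The diary grid does not appear in the text, so whether it has room for five weeks is unknown. Consent pages were removed, so the diary cannot be called the only dosing instruction patients receive.

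**Conclusion.** The point holds in a limited form. For severe hepatic impairment and cirrhosis, the letrozole entry conflicts with the diary, and with item 6 as literally worded. The readings differ by a factor of about two in tablets (28 against 14 over 28 days). This rests on such a patient passing eligibility and being prescribed letrozole, which the criteria do not rule out by name; the count may be zero of 37. It would be wrong to read the conflict as affecting letrozole patients in general.

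The diary's fixed four weeks against a three-to-five-week window ending at surgery is an ambiguity, not a contrary dosing order. It needs no liver disease to arise, and it touches the specimen that supplies the primary endpoint. The food wording is a minor mismatch.

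The sample size of 37 and the primary binomial test are unaffected.

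**What to change.** 1. Reconcile the letrozole hepatic entry, Section VI item 6, Appendix 1 and the hepatic eligibility criteria in Section III so that they state the same thing. Say whether item 6 concerns toxicity only, whether patients in the subgroup are eligible, and whether the subgroup line means class C, cirrhosis, or both together.
2. Make the diary specific to the prescribed agent, so that it and the Study Drugs entry state the same frequency and food instruction.
3. Make the diary's period wording agree with Treatment Plan item 7 and Study Calendar footnote 9, and check that the form has room for the longest treatment the protocol keeps.

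Which dosing or eligibility rule is right is for the sponsor to decide. The cost is a wording amendment and a revised patient form; reconciling the wording does not itself require more visits, tests or patients.

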Resistance to endocrine therapy is common in HR+ breast cancers that **overexpress HER2**.¹⁵ Many studies have reported cross-talk between ER and receptor tyrosine kinases (RTKs), such as HER1 and HER2, which are members of the human epidermal growth factor receptor (HER/EGFR/ERBB) family.^{16,17} Overexpression of these receptors in a subset of ER+ breast cancers suggests that tyrosine kinase signaling drives proliferation and evasion of apoptosis in these cancers, representing either a primary mechanism in the case of innate resistant tumors or a switch in driving mechanisms to evade the action of endocrine therapy in tumors with acquired resistance.^{18,19} Turnbull et al.²⁰ studied gene expression changes in breast cancer tumors treated with neoadjuvant aromatase inhibitors to assess association of proliferation genes with clinical and molecular responses. Proliferation-associated genes were significantly downregulated in tumors responding to endocrine therapy and upregulated in nonresponders by as early as two weeks. We recently reanalyzed this data (**[name] et al; in preparation**) to study 53 RTKs and to assess changes in mRNA levels at two weeks and three months of neoadjuvant endocrine therapy. In many tumors, mRNA encoding EGFR or HER2 increased fourfold or more (note log scale; Figure 1).

However, it is unknown to what extent such increase occurs in patient tumors at the level of HER-protein expression. This is important since HER-targeted agents work on proteins.

[figure not shown]

Figure 1. Changes in mRNA levels in EGFR and HER2 at Day 14 and Day 90 of endocrine treatment.

[figure not shown]

Figure 2. Patient-derived Luminal B MCW2 human breast cancer shows upregulation of HER2 protein in Tam-resistant line, including lung metastases.

Intriguingly, tamoxifen treatment induces increased HER2 protein in cancer cells of a patient-derived breast cancer model analyzed *in vivo* (Figure 2). Furthermore, while parental PDX model is unresponsive to trastuzumab (anti-HER2 antibody), the tamoxifen-resistant tumors (TamR) with elevated HER2 expression were highly responsive to trastuzumab when tested in mice (Figure 3). **Our study will evaluate if treatment-associated changes in protein expressions in HER family of RTKs correlate with tumor responses.**

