- c) Similarly, appropriate two sample tests will be used to test differences in biomarkers between the high difference in Ki-67 and low difference in Ki-67 groups. We will use the appropriate kind of regression instead of two sample tests, to test differences in biomarkers between the high difference in Ki-67 and low

difference in Ki-67 groups if we need to adjust for covariates.

- d) Additionally, regression analysis will also be done to evaluate the changes in the biomarkers and their association with patient specific covariates, such as age, race and other relevant predictors of interest.

Radiographic responses will be assessed by WHO criteria. Radiographic response rates will be measured as the rate of complete response (CR) or partial response (PR) in patients treated with neoadjuvant endocrine therapy. Complete response is defined as the resolution of tumor on post-treatment imaging as compared with pretreatment imaging, while partial response is defined as 50% reduction in tumor size on post-treatment imaging, as compared with pretreatment imaging. We will estimate the rates of response with 95% confidence intervals. We will use logistic regression (and other generalized linear models as appropriate) to measure association between the response rates and patient specific covariates such as age, race and other relevant predictors of interest.

We will use a family type I error rate of 0.05 significance throughout with Bonferroni adjustments for multiple testing wherever appropriate, so that the overall family type I error rate is maintained.

Sample Size and Power Calculation

To achieve at least 80% power at significance level of 0.05, when testing the one sided one sample hypothesis that the proportion of tumors with HER protein upregulation with neoadjuvant endocrine therapy is at least 50% versus the null hypothesis that the proportion is no larger than 30%, **the minimum number of patients required is 37.**

Early Stopping for Futility

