Early stopping for futility and interim analysis in clinical trials are done to ensure safety of the patients and prevent any unnecessary intervention. This is an exploratory study to understand changes in tumor biology with neoadjuvant endocrine treatment. All study biomarkers including changes in HER family of RTKs are being studied to assess responses and development of endocrine resistance. In this study, patients are being treated with endocrine therapy in the neoadjuvant setting for a short duration of time (4 weeks +/- 1 week) without causing any significant delay in their surgery. They will be treated with the same endocrine therapy in the adjuvant setting for at least 5 years which is standard of care. These drugs are routinely used in neoadjuvant setting in patients deemed to be poor surgical candidates or requiring a delay in surgery for variety of reasons and is considered a safe approach with minimal risk to the patients particularly when used for a short duration as done in this study.

The primary objective of this study is to assess changes/upregulation of one or more HER proteins (HER1-4) after neoadjuvant endocrine treatment. Given the exploratory nature and small sample size of this study, we may not see enough upregulation of HER

proteins to meet statistical significance. Up regulation or lack thereof of HER proteins is not a known prognostic factor for patient outcomes at this time and will not impact the safety or clinical management of these patients. Interim analysis and stopping for futility is not indicated in this setting of an exploratory study where the goal is to understand changes in tumor microenvironment to learn more about tumor responses or lack thereof to endocrine treatment. We expect to get important preliminary data from this exploratory study for future follow up clinical trials.

Missing Data management: Observed data will be included in listings, summary tables and statistical analysis, with counts and proportions of missing data, if any. The only likely source of missing data in our study is the absence of some biomarker information due to lack of tissue specimens. As already mentioned, we will attempt to obtain additional biopsy tissue to complete the information, but in case this is not feasible, the evaluation of these biomarkers will be done dropping the missing samples from the analysis. This missed data is likely to be at random and there will be no imputation of missing data.

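### The any-of-four HER primary endpoint has no scoring scale or rise cut-off, and its unsourced 30% null is described as an untreated rate in a study where every patient is treated

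*Combined protocol and SAP*

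**What the plan says.** Section VII (Statistical analyses) hypothesises that "expression of one or more HER proteins (HER1-4) will be upregulated in at least 50% of tumors" after four weeks of therapy, "as compared to upregulation in 30% or less of tumors without the therapy". The Statistical Methodology row of the Protocol Summary repeats this. Item a) then sets an exact one-sample binomial test against "the null hypothesis that the proportion of upregulated HER proteins is not greater than 30" per cent. Sample Size and Power Calculation states the alternative by tumour: "the proportion of tumors with HER protein upregulation with neoadjuvant endocrine therapy is at least 50" per cent, one-sided 0.05, at least 80% power, 37 patients.

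On measurement, Table 1 speaks only of increased HER1-4 protein levels. Pathologic Evaluation item 3 says only that protein is quantified on slides by optimised immunohistochemistry. Ki-67 is treated differently: "The change in Ki-67 expression will be dichotomized, as a categorical variable with" an increase of 10% or more as high. Early Stopping for Futility restates the primary objective as to "assess changes/upregulation of one or more HER proteins (HER1-4) after neoadjuvant endocrine treatment", again without an amount.

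The only size named for a HER rise is in the Background, and it concerns mRNA: "In many tumors, mRNA encoding EGFR or HER2 increased fourfold or more". The same section says that the extent of any increase at protein level is unknown. Treatment Plan item 7 gives endocrine therapy to every enrolled patient.

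**The concern.** Two things are missing, and each affects what the primary result can mean.

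First, the event is not defined. Whether 30% is a low or a high bar, and whether 50% can be reached, depends on how large a rise must be and on what scale. With four proteins and an any-of rule, a loose definition could pass 30% from measurement scatter alone, while a strict one could keep a real rise well below it. The same classification feeds the Ki-67 comparison in item b). While it is open, it could also be settled after the data are seen.

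Second, the 30% is presented as what would happen in untreated tumours. The study has no untreated group and cites no source for such a rate, and the Background says protein-level behaviour is unknown. A reader of a significant result would be led to a contrast that the design does not contain.

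The frequency is meant to inform a randomised anti-HER trial (Primary Objective) and to help select its patients (Future Directions), so its definition matters even if the p-value is set aside.

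**Working it through.** **1. The plan's own figure.** Inputs from Sample Size and Power Calculation: null 0.30, alternative 0.50, one-sided 0.05, power 0.80. The arcsine formula gives h = 2·asin(√0.5) − 2·asin(√0.3) = 0.4115 and n = ((1.645 + 0.842)/0.4115)² = 36.5, so 37. The stated number is reproduced.

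**2. The exact rule at 37.** P(X ≥ 16 | 0.30) = 0.0604 and P(X ≥ 17 | 0.30) = 0.0295. The exact 0.05 test therefore rejects at 17 or more (17/37 = 45.9%), with size 2.9%. This holds for any definition of a success fixed beforehand.

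**3. How the success rate depends on the cut-off.** The documents give no scatter, correlation or effect size, so what follows is assumed. Let each protein's pre/post difference be normal with SD 1 and common correlation ρ, and let c be the cut-off in SDs. The any-of-four rate is 1 − ∫ φ(u)·Φ((c − √ρ·u)/√(1 − ρ))⁴ du. For ρ = 0 this is 1 − Φ(c)⁴; at c = 0 it is 1 − 0.5⁴ = 0.938.

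No drug effect, ρ = 0 / 0.5 / 0.9:

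| Cut-off | Tumours counted | Chance of ≥17/37 |
|---|---|---|
| any rise | 93.8 / 80.0 / 63.1% | 100 / 100 / 98.9% |
| 1 SD | 49.9 / 37.3 / 24.4% | 74.0 / 18.0 / 0.4% |
| 2 SD | 8.8 / 7.2 / 4.3% | all below 0.01% |

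One protein raised by an assumed 1 SD, the other three unchanged:

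| Cut-off | Tumours counted | Chance of ≥17/37 |
|---|---|---|
| any rise | 98.0 / 90.7 / 84.3% | all above 99.9% |
| 1 SD | 70.2 / 57.7 / 50.2% | 99.9 / 94.6 / 75.2% |
| 2 SD | 21.5 / 18.5 / 15.9% | all below 0.1% |

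At 2 SD the assumed effect at least doubles the rate (8.8% to 21.5%, or 4.3% to 15.9%), yet the test against 30% almost never rejects.

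**4. Intermediate cut-offs.** In the same model, a cut-off of 1.25 SD with ρ = 0.5 gives 27.1% with no effect (chance of rejection 1.1%) and 46.7% with the effect. A cut-off of 1.5 SD with ρ = 0 gives 24.2% and 43.8%. Such rules are roughly consistent with the plan's 30% and 50%.

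**5. Unit.** Item a) speaks of HER proteins; the hypothesis and the sample size speak of tumours. If the four proteins were independent, 30% of tumours would correspond to 1 − 0.7^(1/4) = 8.5% of proteins, and 50% to 1 − 0.5^(1/4) = 15.9%. If they moved fully together, the two rates would be the same.

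**The case against.** A fixed null rate is legitimate in a single-arm study, and the test keeps its size. The untreated label stands only in the hypothesis sentence; the null in item a) and in the sample size section omits it. The study is exploratory and says that significance may not be reached. It states that HER results will not alter safety or clinical management, and nothing makes the later trial conditional on rejecting 30%. It also promises that "values of all biomarkers pre and post-treatment, response measures will be summarized". All of this stands, and it limits the harm. It does not supply a definition of the tested event or support the comparison with untreated tumours.

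Several stronger readings are tempting but not supported:

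- *Type I error is inflated.* If the true background rate were 40%, the test would reject 28.2% of the time. But 40% lies outside the null of 30% or less, so this is not a type I error of the stated test. It is an error only if rejection is read as a drug effect.
- *30% and 50% are the wrong pair.* Step 4 shows cut-offs that roughly fit them.
- *Scatter alone would make the trial positive.* The any-rise figures need a continuous score without ties. On an ordinal immunohistochemistry score, unchanged tumours tie and the rate falls by an unknown amount.
- *The same percentages cannot apply to proteins and tumours.* That depends on the proteins not moving together. A binomial test sized at 37 patients fits one result per case, so item a) is best read as loose wording.
- *Increased, upregulated and changed are rival definitions.* They read as ordinary synonyms; the gap is that none carries an amount.

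**Conclusion.** The point holds and should be fixed; it does not invalidate the test. The plan does not say what makes a HER protein upregulated, and it attaches an untreated meaning to a 30% that has no source and no comparison group. The test is sound for the bare null at 2.9%, provided the rule is fixed in advance. What it cannot support is a claim of a rise over untreated tumours.

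Under the assumed scatter and with no drug effect, the choice of cut-off alone moves the chance of a significant result from about 99% or more to practically zero. The model, the correlations and the 1 SD effect are assumptions. The numbers show dependence on the missing cut-off; they do not estimate what this trial will find. The absence of a definition and of a source rests on the text alone.

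**What to change.** 1. In the Protocol Summary and in Section VII, delete the last three words of the clause that attributes the 30% to untreated tumours. Call 30% an assumed benchmark, and do not present rejection as evidence of a drug effect against no treatment.
2. Reword item a) to one yes/no result per patient: upregulated if at least one of HER1-4 rises by at least its pre-specified cut-off between core biopsy and surgical specimen. State which lesion counts when there are several, since Inclusion Criterion 9 allows bilateral and multifocal disease. State also how a patient with only some of HER1-4 measured is classified: Treatment Plan item 10 permits this, and the missing-data paragraph only drops missing samples.
3. Before any slide is read, fix the HER scale and one rise cut-off per protein, and justify or restate both 30% and 50% for those cut-offs.

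Optional: one looser and one stricter cut-off as sensitivity analyses; descriptive counts of rises and falls per protein; and, where feasible, same-run staining of each pair with the existing readers masked to time point.

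The cost is plan wording, with no extra patients unless the restated rates differ from 30% and 50%; the sample size of 37 must then be rechecked. A stricter cut-off will lower the observed frequency. Masking may be partial if core and excision sections can be told apart. A systematic core-to-excision shift is not removed and should be stated as a limitation.
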